4.1.1. Analysis Methods

Continuous data will be summarized in terms of the number of observations, mean, standard deviation (SD), median, minimum, and maximum. The minimum and maximum will be reported to the same number of decimal places as the raw data recorded in the database. The mean and median will be reported to one more decimal place than the raw data recorded in the database. The SD will be reported to two more decimal places than the raw data recorded in the database. In general, the maximum number of decimal places reported shall be four for any summary statistic.

Categorical data will be summarized in terms of the number of patients providing data at the relevant time point (n), frequency counts and percentages. Percentages will be presented to one decimal place. Percentages will be calculated using n (the number of observations with non-missing values) as the denominator.

Unless otherwise specified, analysis of hypotheses will be tested without multiplicity control at a significance level of 0.05. A 2-sided 95% CI will be provided along with the p-value. P-values

which are greater than or equal to 0.001, and less than or equal to 0.999, will be presented to three decimal places. All other p-values which are less than 0.001 will be presented as '<0.001', while p-values greater than 0.999 will be presented as '>0.999'. CIs will be presented to one more decimal place than the raw data.

Unless otherwise specified, variables will be analyzed in the original scale on which they are measured. However, if it is deemed more statistically appropriate, a transformation, such as to the logarithmic scale, may be applied before analysis. The parametric approach will be employed by default for statistical analysis except when nonparametric analysis, such as by a rank-based method, is considered to be more fitting.

For assessments of the primary endpoint, other categorical (binary) efficacy, the Cochran-Mantel-Haenszel (CMH) chi-square test will be used to compare the treatment groups with the following factors:

- previous advanced therapy failure status (yes/no)
- baseline corticosteroid use (yes/no)
- baseline disease activity (MMS: [4 to 6] or [7 to 9]), and
- region (North America/Europe/Other).

The CMH chi-square p-value and the relative risk along with its 2-sided CI will be provided. In addition, the absolute treatment difference in proportions will be provided along with the 2-sided CI estimate. The differences between each treatment group and placebo will also be tested separately using a logistic regression model that controls for at least previous advanced therapy failure status (yes/no) and corticosteroid use (yes/no). If deemed necessary, additional analyses of categorical efficacy variables may be conducted to address sparse data and/or small sample sizes.

Treatment comparisons of continuous efficacy and health outcome variables with multiple postbaseline time points will be made using MMRM analysis. The MMRM will include the following effects and covariates:

- treatment group
- previous advanced therapy failure status (yes/no)
- corticosteroid use (yes/no)
- disease activity (MMS: [4 to 6] or [7 to 9]) at baseline)
- region (North America/Europe/Other)
- baseline value in the model
- visit, and
- the interactions of treatment-by-visit and baseline-by-visit as fixed factors.

The covariance structure to model the within-participant errors will be unstructured. If the unstructured covariance matrix results in a lack of convergence, the heterogeneous Toeplitz covariance structure, followed by the heterogeneous autoregressive covariance structure, will be used. The first structure to yield convergence will be used for inference. The Newton-Raphson with ridging optimization technique will be used to aid with convergence. The Kenward-Roger

method will be used to estimate the denominator degrees of freedom. Type III sums of squares for the LS means will be used for the statistical comparison; the 95% CI will also be reported. Treatment group comparisons with placebo at Week 12 and all other appropriate time points will be tested.

Treatment comparisons of continuous efficacy and health outcome variables with a single postbaseline time point will be made using ANCOVA with the following in the model:

- treatment group
- previous advanced therapy failure status (yes/no)
- corticosteroid use (yes/no)
- disease activity (MMS: [4 to 6] or [7 to 9]) at baseline)
- region (North America/Europe/Other), and
- baseline value.

Type III sums of squares for LS means will be used for statistical comparison between treatment groups. The LS mean difference, standard error, p-value, and 95% CI, unless otherwise specified, will also be reported.

4.1.2. Handling of Dropouts or Missing Data

Intercurrent events (FDA 2017) are events which occur after the study intervention initiation and make it impossible to measure a variable or influence how it should be interpreted. Examples of such events include treatment discontinuation due to death or adverse events (AEs), rescue treatment, and loss to follow-up. The missing data handling methods described below describe how intercurrent events will be used for the different estimands.

4.1.2.1. Non-Responder Imputation (NRI)

The primary outcome is the proportion of patients with clinical remission at Week 12. For this and other categorical efficacy endpoints (for example, clinical remission (week 52), clinical response (week 12, 52), and endoscopic remission (week 12, 52)), non-responder imputation (NRI) will be used for missing clinical assessment values. Specifically, all patients who discontinue from the study at any time prior to week 12 for any reason or fail to have an adequate week 12 efficacy assessment will be considered a non-responder at week 12. Patients who discontinue from the study for any reason at any time prior to week 52 after having enrolled into the Maintenance Period or fail to have an adequate week 52 efficacy assessment, will be considered a non-responder at week 52.

The NRI may be applied at any time point specified for analysis.

4.1.2.2. Mixed-Effects Model for Repeated Measures

For the continuous secondary and exploratory efficacy and health outcome variables, MMRM analyses will be the main method to mitigate the impact of missing data. This approach assumes that missing observations are missing-at-random (missingness is related to observed data) during the study and takes into account both the missingness of data and the correlation of the repeated measurements.

All continuous endpoints will utilize MMRM to patients who permanently discontinued study drug or who were rescued.

4.1.2.3. Modified Baseline Observations Carried Forward (mBOCF)

For patients discontinuing investigational product due to an AE, the baseline observation for the endpoint will be carried forward to the corresponding visit for all missing observations after the patient discontinued study treatment. For patients discontinuing investigational product for any other reason, the last non-missing postbaseline observation before discontinuation will be carried forward to the corresponding visit for all missing observations after the patient discontinued. For all patients with sporadically missing observations prior to discontinuation, the last non-missing observation before the sporadically missing observation will be carried forward to the corresponding visit. Randomized patients without at least 1 postbaseline observation will not be included for evaluation with the exception of patients discontinuing study treatment due to an AE.

The mBOCF method is based on an estimand that handles the intercurrent event of discontinuing study drug due to an AE by defining the patient as not receiving any benefit from study drug after the event. That is the patient is defined as reverting back to baseline regardless of any continuing efficacy benefits they may still have received after the event. For other intercurrent events (e.g., rescue treatment and discontinuation due to reasons other than an AE) or sporadic missingness the “while on treatment” strategy is applied. That is, the endpoint is defined as the last observed value at or before the visit of interest before the patient discontinued study treatment.

4.2. Participant Dispositions

A detailed description of participant disposition will be provided, including a summary of the number and percentage of participants entered into the study and randomized, the number and percentage of participants who complete the study or discontinue, both overall and by reason for discontinuation, and the frequency and percentage of patients who discontinue study treatment. A summary of important protocol deviations will be provided.

4.3. Primary Endpoint Analysis

4.3.1. Definition of endpoint

Rate of clinical remission at Week 12 is the primary efficacy outcome for this study and will be analyzed using the mITT population.

Clinical remission is defined as achieving a rectal bleeding (RB) subscore of 0, and stool frequency subscore (SF) of 0, or 1 with a decrease of ≥ 1 point from baseline, and endoscopic (ES) subscore of 0 or 1, excluding friability. SF and RB subscores are calculated by averaging and rounding the 4-point daily scores over 3 days as described in [6.6](#).

4.3.2. Main analytical approach

The primary objective of this study is to test the hypothesis that treatment with LY3471851 is superior to placebo in inducing clinical remission at Week 12 in patients with moderate to severe ulcerative colitis (UC).

The rates of clinical remission and non-remission will be summarized by treatment group and by the stratification factors, previous advanced therapy failure status (yes/no), baseline corticosteroid use (yes/no), baseline disease activity (MMS: [4 to 6] or [7 to 9]), and region (North America/Europe/Other).

The primary analysis will use the CMH chi-square test to compare LY3471851 to placebo at Week 12. The stratification factors used for CMH test are (a) previous advanced therapy failure status (yes/no), (b) baseline corticosteroid use (yes/no), (c) baseline disease activity (MMS: [4 to 6] or [7 to 9]), and (d) region (North America/Europe/Other). See Section 4.1.1 for details on the methods to be used to test the differences between each active treatment arm and placebo.

Ninety five percent confidence interval along with the p-value for the difference in proportions (LY arm – placebo) for each pairwise comparison will be obtained. For a pairwise comparison, if p-value is less than 0.05, then that LY arm will be considered to be superior to placebo.

A composite strategy is proposed for other intercurrent events including discontinuing study intervention, taking prohibited medications or increase the dose of mandatory stable medications. The NRI methodology described in Section 4.1.2.1 will be applied when any of these events occur.

4.3.3. Bayesian Model Averaging

A Bayesian model averaging will be performed for additional analysis of the clinical remission at Week 12. A Bayesian model averaging (BMA) approach will be used to estimate the dose response relationship. This Bayesian model averaging approach is the Bayesian analog of the MCP-MOD methodology (Bretz et al., 2005), and “the Qualification of the MCP-Mod procedure” (FDA, 2015) is supportive in the use of MCP-MOD or Bayesian model averaging to assist in dose selection decisions.

Bayesian model averaging is a general mixture distribution, where each mixture component is a different parametric model. Prior weights are placed on each model and the posterior model weights are updated based on how well each model fits the data. Let $\mu(d)$ represent the mean of the dose response curve at dose d , $y = \{y_1, \dots, y_n\}$ be the observed data, and $m \in \{1, \dots, M\}$ be an index on the M parametric models described below. Then the posterior of the dose response curve, $\mu(d)$, of the Bayesian model averaging model is

$$p(\mu(d) | y) = \sum_{m=1}^M p(\mu(d) | y, m) p(m | y)$$

$$p(m | y) = \frac{p(y | m)p(m)}{\sum_{m^*} p(y | m^*)p(m^*)}$$

where $p(\mu(d) | y, m)$ is the posterior mean dose response curve from model m , $p(m | y)$ is the posterior weight of model m , $p(y | m)$ is the marginal likelihood of the data under model m , and $p(m)$ is the prior weight assigned to model m . In cases where $p(y | m)$ is difficult to compute, Gould (2019) propose using the observed data’s fit to the posterior predictive distribution as a surrogate in calculating the posterior weights; this is the approach used in this analysis.

4.3.3.1. BMA Analysis and Reporting

BMA will be executed for the proportion of participants who achieve clinical remission at Week 12.

BMA analysis will be summarized by dose and provide

- Observed response
- BMA estimated
 - Mean response
 - Standard error and standard deviation of the mean response
 - 2.5% and 97.5% quantiles
 - Summaries of posterior probability of LY - PBO treatment effect, i.e., $\Pr(\text{LY} - \text{PBO} > \text{EOI})$ where EOI is effect of interest
- Plot that includes observed response, BMA estimated response, 2.5% and 97.5% posterior quantiles

BMA analysis will be summarized by component and model parameter and provide

- Posterior mean
- Standard error and standard deviation of the posterior mean
- 2.5% and 97.5% posterior quantiles of the posterior distribution
- Convergence diagnostics
- Effective sample size
- Prior distributions
- Plot of the fitted BMA
- Plot of the BMA components

4.4. Secondary Endpoints Analyses

4.4.1. Secondary Efficacy Endpoints

4.4.1.1. Definition of Endpoints

In the analyses of secondary efficacy outcomes, no adjustments for multiple testing will be performed unless otherwise specified.

The efficacy assessments of secondary endpoints are shown in the following table:

Table KFAH.3. Efficacy Assessments

Clinical Remission	SF subscore = 0, or SF = 1, and RB subscore = 0, and ES = 0 or 1, excluding friability.
Clinical Response	A decrease in the MMS of ≥ 2 points and $\geq 30\%$ decrease from baseline, and a decrease of ≥ 1 point in the RB subscore from baseline or a RB score 0 or 1.
Endoscopic Remission	Mayo ES = 0 or 1, excluding friability.

Endoscopic Response	A decrease in the Mayo ES of ≥ 1 point compared to baseline.
Symptomatic Remission	SF = 0, or SF = 1 with a decrease of ≥ 1 point from baseline, and RB = 0.
Symptomatic Response	$\geq 30\%$ decrease from baseline in the composite clinical endpoint of the sum of SF and RB subscores.
Histologic Remission	Geboes score < 2 or Geboes subscores = 0 for Grade 2a, 2b, 3, 4, and 5.
Histologic-Endoscopic Mucosal Healing	Geboes score < 2 and endoscopic remission.

Abbreviations: ES = endoscopic subscore; MMS = modified Mayo score; RB = rectal bleeding; SF = stool frequency.

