5.1. Inclusion Criteria

Patients with UC will be included in the study only if they meet all of the following inclusion criteria.

Informed Consent

1. Are capable of giving informed consent as described in [Appendix 1](#), Section 10.1.3, which includes compliance with the requirements and restrictions listed in the ICF and in this protocol, including the contraception requirements.

Note: For the contraception requirements of this protocol, see [Appendix 4](#). Contraceptive use by men or women should be consistent with local regulations regarding the methods of contraception for those participating in clinical studies.

Patient Characteristics

2. Are male or female patients from 18 to 75 years of age, inclusive, at the time of initial screening (Visit 1).

Note: Women of child-bearing potential (WOCBP) must test negative for pregnancy as indicated by a negative serum pregnancy test at the screening visit followed by a negative urine pregnancy test within 24 hours prior to first exposure to study drug.

3. Have venous access sufficient to allow the protocol-required blood sampling.
4. Are willing and able to complete the scheduled study assessments, including endoscopies and daily diary entries.

Disease-Specific Characteristics

5. Have had an established diagnosis of UC of ≥ 3 months in duration before baseline (Visit 2), which includes endoscopic evidence of UC and a histopathology report that supports a diagnosis of UC (see Section 8.1.1.3). Supportive endoscopy and histopathology reports must be available in the source documents.
6. Have moderately to severely active UC as defined by a modified Mayo score (MMS) of 4 to 9 with an endoscopic subscore (ES) ≥ 2 , with endoscopy performed within 14 days before baseline.

Note: The MMS requires accurate documentation of the stool frequency (i.e. baseline prior to onset of UC signs/symptoms OR stool frequency when in remission) as well as

3 days of diary data (of stool frequency and rectal bleeding) in the 7 days preceding the first date of bowel prep, if no bowel prep, day of endoscopy).

Note: The Mayo ES, as determined by the Image Review charter, will be provided to the site prior to randomization to enable determination of the MMS for eligibility.

7. Have evidence of UC extending proximal to the rectum (with ≥ 15 cm of involved colon).
8. Have documentation of
 - 8a. a surveillance colonoscopy (performed according to local standard) within 12 months before baseline for

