8.1. Efficacy Assessments

This study uses components and permutations of the Mayo score¹⁷ to assess UC disease activity for the primary and several secondary endpoints, as defined in the table below.

Complete and accurate daily recording of the Mayo SF and RB subscores by participants in their daily eDiary is necessary for the success of the study. Adequate bowel preparation and an endoscopy with adequate visualization of the mucosa will enable calculation of the Mayo ES.

Endpoint	Definition
Clinical remission	SF subscore = 0, or SF = 1 with a decrease of ≥ 1 point from baseline, and RB subscore = 0, and ES = 0 or 1, excluding friability
Clinical response	A decrease in the MMS of ≥ 2 points and $\geq 30\%$ decrease from baseline, and A decrease of ≥ 1 point in the RB subscore from baseline or a RB score of 0 or 1
Endoscopic remission	Mayo ES = 0 or 1, excluding friability
Endoscopic response	A decrease in the Mayo ES of ≥ 1 point compared to baseline
Symptomatic remission	SF = 0, or SF = 1 with a decrease of ≥ 1 point from baseline, and RB = 0
Symptomatic response	$\geq 30\%$ decrease from baseline in the composite clinical endpoint of the sum of SF and RB subscores
Histologic remission	Geboes score < 2 or Geboes subscores = 0 for Grade 2a, 2b, 3, 4, and 5 (equivalent definitions)
Histologic-endoscopic mucosal healing	Geboes score < 2 AND endoscopic remission

Abbreviations: ES = endoscopic subscore; MMS = modified Mayo score; RB = rectal bleeding; SF = stool frequency.

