6.7. Appendix 7: List of Planned Laboratory Analytes with Reference
Range Sources.....64

7. **References.....68**

Version history

This Statistical Analysis Plan (SAP) for study J1P-MC-KFAH (KFAH) is based on the protocol dated 18Nov2020 and approved prior to unblinding.

Table KFAH.1. SAP Version History Summary

SAP Version	Approval Date	Change	Rationale
1		Not Applicable	Original version

1. Introduction

Study J1P-MC-KFAH is an adaptive Phase 2, randomized, double-blind, placebo-controlled trial of LY3471851 (NKTR-358) in patients with moderately to severely active ulcerative colitis.

There are no changes to the analyses described in the protocol.

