4.4.1.3. Secondary Efficacy Endpoints for the Maintenance Period

Secondary efficacy endpoints for the maintenance period for participants who were responder per IWRS at Week 12, have not permanently discontinued at Week 52, and have achieved at Week 52 include clinical remission, clinical response, endoscopic remission, endoscopic response, symptomatic remission, symptomatic response, histologic remission, and histologic-endoscopic mucosal healing at Week 52.

Analyses will be performed as per the methodology described in Section 4.1.1.

The mITT population will be used for the secondary efficacy outcome analyses.

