4.7. Other Analyses

4.7.1. Efficacy Subgroup Analysis

Subgroup analyses will be conducted on the mITT population for the following:

- Clinical remission
- Clinical response
- Endoscopic remission
- Endoscopic response
- Symptomatic remission
- Symptomatic response
- Histologic remission
- Histologic-endoscopic mucosal healing

The following subgroups (but not limited to only these) will be evaluated:

- Gender
- Age category
- Body weight
- Race
- Geographic region
- Baseline disease severity and activity
- Duration and location of disease

- Previous systemic therapy
- Previous advanced therapy, and
- Concomitant therapy for UC.

Descriptive statistics will be provided for each treatment and stratum of a subgroup as outlined, regardless sample size.

Each categorical variable will be analyzed individually with a logistic regression model that contains the treatment, the subgroup variable, and subgroup by treatment interaction. The treatment-by-subgroup interaction will be tested at the 10% significant level. Within each subgroup category, the proportion of responders by treatment, treatment differences, and 95% CIs will be displayed.

For continuous variables, MMRM analysis will be performed with subgroup-by-treatment interaction. Within each subgroup, LS means by treatment, LS mean differences, and 95% CIs will be displayed.

If the number of patients in any subgroup category is less than 10% of the total population, only summaries of the efficacy data will be provided. Additional subgroup analyses may be performed as deemed necessary.

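### SAP Table KFAH.3 drops the 1-point stool frequency decrease from clinical remission, so Week 52 remission as written follows a looser rule than Protocol 8.1, although the SAP declares no changes.

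*SAP*

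**What the plan says.** Protocol 8.1 gives one definition of clinical remission, tied to no visit. Its stool frequency part reads "SF subscore = 0, or SF = 1 with a decrease of" at least 1 point from baseline. A rectal bleeding (RB) subscore of 0 and an endoscopic subscore (ES) of 0 or 1 are also required.

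SAP 4.3.1 repeats this for the Week 12 primary endpoint: "stool frequency subscore (SF) of 0, or 1 with a decrease of" at least 1 point.

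SAP 4.4.1.1 introduces Table KFAH.3 as the definitions for the secondary endpoints. Its clinical remission row reads "SF subscore = 0, or SF = 1, and RB subscore = 0, and ES = 0 or 1, excluding friability", with no reference to baseline. The symptomatic remission row of the same table keeps the condition: "SF = 0, or SF = 1 with a decrease of" at least 1 point from baseline.

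SAP 4.4.1.3 lists the maintenance endpoints for participants who "have achieved at Week 52 include clinical remission, clinical response, endoscopic remission" and others. The Week 12 secondary list in SAP 4.4.1.2 does not contain clinical remission. SAP 4.7.1 states that "Subgroup analyses will be conducted on the mITT population for the following" and puts clinical remission first, without naming a visit or a definition.

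SAP Section 1 states: "There are no changes to the analyses described in the protocol". SAP 4.9, the section on changes to the planned analyses, deals only with protocol deviations.

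**The concern.** The SAP holds two rules under one name. The row in Table KFAH.3 is the only explicit definition of clinical remission in the SAP's secondary endpoint section, and Week 52 is its only secondary use. A programmer who follows the SAP section by section would apply the protocol rule at Week 12 and a looser one at Week 52.

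A participant whose stool frequency has not improved, or has worsened from 0 to 1, could then be reported in clinical remission at Week 52. The same participant would fail symptomatic remission under the next rows of the same table. The reported Week 52 endpoint would not be the protocol's, Week 12 and Week 52 remission would not be comparable, and nothing in the SAP would tell a reader so.

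**Working it through.** The plan states no figure to reproduce on this point. The check compares the definitions and then counts where they can disagree.

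**Definitions side by side**

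| Source | Used for | SF = 1 counts if |
|---|---|---|
| Protocol 8.1 | all time points | SF fell by at least 1 from baseline |
| SAP 4.3.1 | Week 12 primary | SF fell by at least 1 from baseline |
| SAP Table KFAH.3, clinical remission | secondary (Week 52) | always |
| SAP Table KFAH.3, symptomatic remission | secondary | SF fell by at least 1 from baseline |

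The RB and ES conditions for clinical remission are the same in all three definitions.

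**Inputs for the count**

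- Eligibility (Protocol 5.1, criterion 6): active disease "as defined by a modified Mayo score (MMS) of 4 to 9 with an endoscopic subscore" of at least 2. No minimum SF is set.
- SF, RB and ES are integers from 0 to 3 (Protocol Appendix 9). SAP 6.6 rounds SF and RB to integers.

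**Step 1: eligible baselines**

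- ES = 2 needs SF + RB of at least 2: 16 − 3 = 13 profiles.
- ES = 3 needs SF + RB of at least 1: 16 − 1 = 15 profiles.
- Total: 13 + 15 = 28.
- With SF = 0: 2 (ES 2) + 3 (ES 3) = 5. With SF = 1: 3 + 4 = 7. So 12 profiles have SF of 0 or 1, and 28 − 12 = 16 have SF of 2 or 3.

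**Step 2: baseline/end pairs that count as remission**

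- Protocol 8.1: end SF 0 gives 28 × 2 = 56 pairs (ES 0 or 1). End SF 1 gives 16 × 2 = 32. Total 88.
- Table KFAH.3: 28 × 4 = 112 (SF 0 or 1, ES 0 or 1).
- Difference: 112 − 88 = 24 pairs, which is 12 baselines × 2 end states (SF 1, RB 0, ES 0 or 1).
- All 24 count under Table KFAH.3 only and none under the protocol only. SF is unchanged in 7 × 2 = 14 and worse in 5 × 2 = 10.

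**Step 3: can these participants be in the Week 52 analysis?**

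The Week 52 comparison concerns Week 12 Responders. The two end states have a modified Mayo score (MMS) of 1 or 2. From the lowest eligible baseline MMS of 4, the smallest fall is 4 − 2 = 2 points, or 50%, and RB is 0. Every one of the 24 pairs therefore meets the clinical response definition. A participant in such a state at Week 12 is a responder and may be in the same state at Week 52. The restriction excludes none of the 12 baseline profiles.

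**Step 4: consistency with the other endpoints**

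Under the protocol wording, clinical remission is exactly symptomatic remission plus endoscopic remission. Under Table KFAH.3 that identity fails in all 24 pairs. Example: baseline SF 1, RB 1, ES 2 (MMS 4) and Week 52 SF 1, RB 0, ES 1. By the table, this participant is in clinical remission but not in symptomatic remission.

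**Step 5: weight of one reclassified participant**

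Using the planned arm sizes in SAP Section 5:

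- placebo, about 40: 100/40 = 2.5 points
- active arm of 40, 60 or 80: 2.5, 1.7 or 1.25 points

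These are minimum steps. They are larger if only Week 12 Responders form the denominator.

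**The case against.** The strongest reply is that the documents taken together already point to the protocol rule. Protocol Section 3 sends the reader to Section 8.1 for both primary and secondary definitions, the defining sentence in SAP 4.3.1 names no visit, and the SAP says nothing has changed. On that reading one table row is a slip that a careful programmer would query. This stands as an account of intent. It does not settle which text governs, because the table is expressly the one for secondary endpoints.

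A second reply is that the clinical and symptomatic remission rows define different endpoints, so a difference between them is not in itself a contradiction, and no passage says that one must imply the other. That is fair. The contradiction is between Table KFAH.3 on one side and Protocol 8.1 and SAP 4.3.1 on the other. The symptomatic remission row is evidence that the omission was accidental.

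Third, the counts say little about size. Twelve of 28 profiles does not mean that 12 in 28 participants are affected, and the percentage steps are simply 100 divided by the arm size. Both points are correct.

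Finally, the reach is narrow: one of eight binary Week 52 endpoints, in a Phase 2 trial without multiplicity control. That limits the priority of the correction but does not remove the need for it.

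**Conclusion.** The concern holds. As written, Table KFAH.3 gives Week 52 clinical remission a strictly looser rule than Protocol 8.1, and the SAP does not declare it. The two rules differ in 24 baseline/end combinations arising from 12 of 28 eligible baseline profiles, always in the direction of more remissions. It reads as a drafting omission, and it should be fixed before the Week 52 derivation is programmed.

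The counts rest on integer subscores and the stated eligibility range, and they count possible score profiles without weighting them by frequency. How many participants would be reclassified, and whether the LY3471851–placebo difference would grow or shrink, cannot be determined from the documents. The subgroup analyses in SAP 4.7.1 may also be affected, since they do not say which rule applies. The Week 12 primary endpoint, its power, the Bayesian model averaging, the interim analyses and the Week 12 responder classification are not affected.

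**What to change.** In the clinical remission row of Table KFAH.3, make SF = 1 conditional on a fall of at least 1 point from baseline, as in Protocol 8.1 and SAP 4.3.1. Add a sentence stating that this single definition applies at all time points and in the subgroup analyses of SAP 4.7.1. With that change the 24 discordant combinations fall to 0.

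The cost is one SAP line and one derivation rule, with no protocol amendment. Week 52 remission rates may come out slightly lower than under the table as it stands.
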